## 3.3.4. Missing Data Conventions

Cohort 2 patients with missing data at Day 0 will use the Screening visit value as their Day 0 result. Similarly, patients with missing data at Screening will use the Day 0 visit value as their Screening result. No Screening or Day 0 data will be imputed for Cohort 1 patients.

Unless otherwise specified, missing data for subsequent visits will be considered missing at random and will not be imputed. If necessary, imputation of partial dates may be performed during the data analysis and will be documented (e.g., missing month=July; missing day=15).

The **Missing Equals Failure (MEF)** imputation technique will be applied to the viral load measures (log10 copies/mL and copies/mL) only. If a viral load measurement is missing at any scheduled visit, the value will be replaced with the baseline viral load measurement. Also, all visits after a confirmed virologic failure will be imputed as failures (replaced with the baseline measurement) for all study visits even if the patient discontinued early.

The Last Observation Carried Forward (LOCF) imputation technique will be applied to the CD4+ T-Cell Counts (cells/mm^3) only. If a CD4+ T-Cell Count is missing at any scheduled visit, the value will be replaced with the most recent previous non-missing value.

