	
12. Any clinically significant Grade 3 or 4 laboratory abnormality according to the Division of AIDS (DAIDS) grading scale, except for the following asymptomatic Grade 3 events:
 
 ➤ triglyceride elevation ➤ total cholesterol elevation

Study Design:
	
This Phase 3, multicenter, expanded access study will evaluate the safety and tolerability of ibalizumab in treatment-experienced patients infected with MDR HIV-1. Patients will be enrolled in one of two Cohorts (Cohort 1 and Cohort 2):
 
Cohort 1 (continuing treatment)
 
 ■ Patients will continue on an ibalizumab-containing regimen at their current dosage in combination with a current OBR. 
Cohort 2 (initiating ibalizumab)
 
 ■ On Day 0 patients will receive one 2,000 mg dose (loading dose) of ibalizumab. An OBR that is selected based on resistance test results and antiretroviral history will be initiated on Day 0 and must include at least one agent to which the patient's virus is susceptible. ■ Beginning at Day 14, 800 mg of ibalizumab will be administered every 2 weeks through the remainder of the study. 
Virologic failure is defined as two consecutive measurements beginning at Week 24 or later if less than a 0.5 log₁₀ decline in viral load from Baseline viral load.
 
Patients may be discontinued from the study:
 
 ■ At the patient's or investigator's request ■ If the patient becomes pregnant ■ For protocol violation ■ For experiencing virologic failure ■ For treatment-related serious or intolerable adverse events (AEs) (DAIDS criteria, see Appendix B) ■ For toxicity (defined as two consecutive laboratory results, at least 14 days apart, with a CD4⁺ cell count below 200 cells/mm³ that also represents a 50% reduction from the baseline CD4⁺ cell count) ■ Upon commercial availability of ibalizumab

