9.1 General Methodology

The data collected are intended primarily for clinical review and interpretation. The analysis of study data will be primarily descriptive, with emphasis on tabular and graphical displays. Descriptive statistics will be used to guide decisions as to the clinical relevance of findings. Unless otherwise stated, p-values will be determined only if they appear to be warranted from the summary statistics.

For continuous data, descriptive statistics will be presented as number of patients (n), mean, standard deviation, median, minimum, and maximum. For categorical data, the frequency and percentage of patients in each category will be presented. Percentages will be based on non-missing data unless otherwise specified.

Data will be described and analyzed using the SAS System Version 9.3 or later (SAS Institute Inc., Cary, NC, SAS System). Individual patient data will be presented in patient data listings.

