9.2 Populations for Analysis

9.2.1 Efficacy Populations

9.2.1.1 Intent-to-Treat Population

The ITT population is defined as all patients enrolled into the study. Patient disposition will be based on the ITT population. The ITT Analysis Population will be used for the primary analysis at Day 7. Patients with missing effectiveness data at Day 7 will have their effectiveness set to failure for all dichotomous effectiveness variables. This will be referred to as the MEF analysis.

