9.2.1.2 Modified Intent-to-Treat Population

The modified intent-to-treat (mITT) population is defined as all ITT patients who received at least one dose of study drug. The mITT Analysis Population will be used for a supportive effectiveness analysis and will include all data without imputing values for missing data.

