## 3.2. Analysis Populations

## 3.2.1. Intent-to-Treat (ITT) Population

The ITT population is defined as all patients enrolled into the TMB-311 study. The ITT Analysis Population will be used for the patient disposition, demographic and physical characteristics, and efficacy analyses.

If there are ITT patients who do not receive at least one complete dose of study drug, then a modified ITT (mITT) Analysis Population will be used for a supportive effectiveness analysis.

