**CONFIDENTIAL** 

# **Notes Applicable to All Listings**

#### General Programming Notes:

- 1. There are a few listings that might fit as they are or might have to be split once we see the output with actual data.
- 2. All listings should start with and be sorted by Patient ID (concatenation of site number and patient number) and then visit date as appropriate.
- 3. If columns with specific text should be widened due to the amount of text, it is up to the programmer's discretion. However, please keep to the industry standard margin of 1 inch on bottom and sides and 1.25 inches on the top. Font is Courier New 8 point.
- 4. For all dates used, character format dates to capture partial dates. Use dashes where a month or day is missing. If entire date is missing just leave blank. i.e., JAN2011 or 01-2011.
- 5. If a programming note appears on the mock listing indicating that the footnote should appear only on the first page, this means the first page of output contains all footnotes and ONLY footnotes. All subsequent pages contain data with one footnote that says "Refer to page 1 for footnotes".
- 6. Some of the mock tables display numbers rather than x's. The numbers are meaningless and are for example only. Where visit names are displayed in tables, these are examples as well. Correct visit names for the TMB-311 study should be displayed in the actual output.
- 7. Each listing should include all applicable data, even if only a subset of the full set of treatment groups is displayed in the mocks. And unlike the tables and graphs, the listings should also include the 2 PI-IND rollover patients.
- 8. Sort each listing by Treatment and then Patient ID where applicable.

Listing 16.2.1.1

Patient Disposition

Treatment	Patient ID Sc	reened	ITT Population [1]	SAF Population [2]	
C1:301/800mg	311-XX-XXX	YES	YES	YES	
C1:202/800mg	311-XX-XXX	YES	YES	YES	
C1:202/2000mg	311-XX-XXX	YES	YES	YES	
C2:800mg	311-XX-XXX	YES	YE:	S YES	

Intent-to-Treat (ITT) Population consists of all patients enrolled into the study.

Programming note: Add the mITT population if analyst decides it is needed later.

Westat (Created on DDMMYYYY)
S:\TMB311\DA\SAS\L PATDISP.SAS

Safety (SAF) Population consists of patients receiving at least one partial dose of study drug.

Listing 16.2.1.2 Study Discontinuation

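### The SAP fills missing viral loads with baseline for mean change as well as response, and no longer assures the protocol's un-imputed supportive analysis

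*SAP*

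**What the plan says.** **Imputation rule.** Protocol 9.2.1.1: "Patients with missing effectiveness data at Day 7 will have their effectiveness set to failure for all dichotomous effectiveness variables". For later visits the protocol has only the general default in 9.1: "Percentages will be based on non-missing data unless otherwise specified". SAP 3.3.4 goes further: "If a viral load measurement is missing at any scheduled visit, the value will be replaced with the baseline viral load measurement". It applies this to viral load on the log10 and copies/mL scales, and SAP 4.4 carries it into the efficacy analyses without exempting means. Mean change and mean level are then reported in SAP 4.5.2.1, 4.5.2.2 and 4.5.3.

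**Supportive analysis.** Protocol 9.2.1.2 commits to an mITT analysis that "will include all data without imputing values for missing data". SAP 3.2.1 makes it conditional: "If there are ITT patients who do not receive at least one complete dose of study drug, then a modified ITT" population is used for a supportive analysis. Nothing there says that analysis is un-imputed. The programming note to Listing 16.2.1.1 reads: "Add the mITT population if analyst decides it is needed later".

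**Exits.** The Protocol Summary (Study Design) lists, among the reasons a patient may be discontinued, "Upon commercial availability of ibalizumab". Protocol 5.3.3 lets the sponsor close the study for that or for administrative reasons. The only rule in SAP 3.3.4 that speaks of visits after discontinuation concerns confirmed virologic failure, where failure is imputed "for all study visits even if the patient discontinued early".

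**The concern.** Counting a missing result as failure is a familiar convention for a responder rate. Putting the baseline value into a mean is different: it adds a measured-looking zero change for a patient who may have been suppressed, even when a patient still on study simply missed one sample. The SAP also extends the secondary endpoints to Cohort 1 (4.5.2). For rollover patients from TMB-202 and TMB-301, Baseline comes from the earlier study (3.3.3), so one missed sample restores that older value.

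The un-imputed analysis is what would let a reader see how much of a late result comes from the fill. If every patient receives one complete dose, the SAP text requires no such analysis.

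This is an access study that foresees ending when the drug is marketed. A literal reading of the rule would enter patients who leave while responding as non-responders with zero change at every remaining visit to Week 144. The results at stake are the durability displays from Week 24 onward.

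**Working it through.** The plan gives no figure of its own on this point, so the check is of scope and of the arithmetic effect of the rule.

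**1. Scope.** The protocol rule covers one visit (Day 7) and one type of variable. Tables 3-5 and 3-6 schedule Cohort 2 viral load after Day 0 at Day 7, Day 14 and Weeks 4, 6, 8, 12, 16, 20, 24, 28, 36, 48, 60, 72, 84, 96, 108, 120, 132 and 144. That is 20 visits, 19 of them after Day 7. Response proportions are tabulated at seven key visits (Day 7 and Weeks 24, 48, 72, 96, 120 and 144); means and graphs cover more.

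**2. Effect of the fill.** Let m be the share missing, μ the mean change and p the response rate among those with data.
- Imputed mean = (1-m)μ + m×0 = μ(1-m)
- Imputed response = p(1-m)

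**3. Scale, from TMB-301 (Protocol 1.2).** 31 of 40 patients completed Week 25, so 9/40 = 22.5% did not. The reported Week 25 percentages are 43 (<50 copies/mL), 50 (<200 copies/mL), 55 (≥1 log10) and 48 (≥2 log10). Among single denominators from 20 to 40, only n = 40 gives whole counts that round to all four. Assume every responder was a completer:

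| Count | Over 40 | Over 31 | Gap (points) |
|---|---|---|---|
| 17 | 42.5% | 54.8% | 12.3 |
| 20 | 50.0% | 64.5% | 14.5 |
| 22 | 55.0% | 71.0% | 16.0 |
| 19 | 47.5% | 61.3% | 13.8 |

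For mean change the reported reduction is 1.64 log10, and its handling of missing data is not stated.
- If 1.64 is un-imputed, the imputed value is 1.64 × 31/40 = 1.27, a gap of 0.37.
- If 1.64 is already imputed, the completers' value is 1.64 × 40/31 = 2.12, a gap of 0.48.

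Neither column is the true value. The table shows only how far the two conventions can differ at this level of missingness.

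**4. Visits after commercial or closure exit, read literally.** Let g be the share who have left for those reasons, with leaving independent of response (assumption). The factor is (1-g). Taking -1.64 log10 and 55% as assumed on-study values:

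| g (assumed) | Mean change | Response |
|---|---|---|
| 0 | -1.64 | 55.0% |
| 10% | -1.48 | 49.5% |
| 22.5% | -1.27 | 42.6% |
| 40% | -0.98 | 33.0% |
| 60% | -0.66 | 22.0% |

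If instead all leavers were responders, the rate would be p - g. At g = 10% that is 55 - 10 = 45%.

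**5. Why an exclusion must treat everyone alike.** Under the same independence, dropping only the responders who leave gives p(1-g)/(1-pg). At p = 0.55 and g = 0.4 this is 0.33/0.78 = 42.3%, still below 55%. Dropping all leavers alike gives p at every g.

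**The case against.** The strongest reply is that the SAP made a permitted and conservative choice. The protocol default on percentages yields where something else is specified, and SAP 3.3.4 specifies it. Protocol 1.2 already describes a missing-equals-failure analysis of the Phase 2b trial at Week 24 as its most stringent. Entering baseline works against the drug, whereas observed means favour patients who stay. This stands for later response rates. It does not cover means, and it does not release the SAP from the unconditional commitment in Protocol 9.2.1.2.

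A second reply is that if every enrolled patient is dosed, mITT equals ITT and the condition in SAP 3.2.1 loses nothing. That is true of the population. What is lost is the statement that values are not imputed.

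Third, some of the SAP's mock displays are not in the public copy. The CD4 listing (16.2.6.2) shows un-imputed and imputed values side by side, and viral load displays may do the same. This stands as a limit: the claim concerns the SAP text only. A listing would in any case not be the supportive analysis.

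A reader might also infer that the SAP contradicts itself on post-exit visits, because 4.5.2.1 and 4.5.2.2 restrict results to visits where viral load was assessed. The documents do not support that. The phrase follows a visit list that differs by cohort (Day 7 is for Cohort 2 only), and schedules do differ: Week 84 viral load appears only in the Cohort 2 table. It reads more naturally as schedule wording than as a rule on exits.

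**Conclusion.** The point holds in two parts and conditionally in a third.

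- **Means are imputed.** The SAP puts baseline values into viral load means at any scheduled visit, which the protocol does not provide for.
- **The un-imputed supportive analysis is not assured.** The SAP attaches a condition and omits the no-imputation wording.
- **Post-exit visits are filled on a literal reading.** The effect is about (1-g), if leaving is independent of response. The documents give no g for TMB-311, and there is no effect at g = 0.

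The gap of 12 to 16 points, or 0.37 to 0.48 log10, rests on TMB-301 counts, on all responders being completers and on 22.5% non-completion. A reader might take it as an estimate of bias from commercial or closure exit. It is not: it reflects general non-completion over about 25 weeks in another study. Nor do the documents support calling the extension of missing-equals-failure to later response rates an error.

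Consequences are bounded. The study is descriptive with no formal testing (SAP 3.4.2), and exit reasons are tabulated (SAP 4.1). The snapshot table separates responding leavers and on-study missing data (SAP 4.5.2.3). The Day 7 primary endpoint is essentially unaffected, because the SAP and protocol rules agree for that response.

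**What to change.** (a) In SAP 3.2.1 and 4.5.2, restore the un-imputed supportive viral load analysis without condition. Include mean log10 change and the number with data at each visit, shown beside the baseline-imputed version.

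(b) In SAP 3.3.4, state that missing viral loads at visits falling after a patient's exit for commercial availability or study closure are not imputed, and show the number excluded at each visit. Keep every observed value. Apply the exclusion to responders and non-responders alike, and say how it fits with the existing rule for visits after confirmed virologic failure. Keep the version that counts all missing values as failure as a sensitivity table.

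**Cost.** SAP wording and one extra table set. Late denominators become smaller. Observed means describe patients still on study and favour them, so the un-imputed version supports the imputed one and does not replace it. Part (b) needs a confirmed exit code or closure date: Protocol 5.3.2 has the reason for exit recorded, but the reason lists in Protocol 5.3.1 and SAP 2.1 do not name commercial availability.

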## 4.4. Efficacy

As described in section 3.3.3 of this document, the MEF technique will be applied to the efficacy analyses with regard to imputing missing viral load results as applicable. Note: Prior to calculating change from Baseline in viral load, the log10 value of each measurement will be calculated and will be rounded to one decimal point.

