## 4.5.2.3 Virologic Outcome

## Snapshot Approach

Virologic outcome will be assigned for each patient at each key visit after Week 12 [Weeks 24, 48, 72, 96, 120, and 144/EOS], per the snapshot approach, using the following standard categories:

- 1=Virologic success (≥0.5 log10 decline from Baseline in viral load)
- 2a=(<0.5 log10 copies/mL drop from Baseline in viral load)
- 2b=Discontinued efficacy portion of study because of virologic failure (may still continue safety)
- 2c=Discontinued because of other reasons and the drop from baseline in viral load at the time of discontinuation was <0.5 log10 copies/mL
- 2d=OBR changed
- 3a=Discontinued because of AE or death
- 3b=Discontinued because of other reasons and the drop from baseline in viral load at the time of discontinuation was >=0.5 log10 copies/mL
- 3c=Missing data during the window but on study

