# 3c=Missing data during the window but on study

[3] Failure to achieve/maintain response=Patient does not have >=0.5 log10 decline from baseline(BL) by Week 12 on study drug OR patient has a 0.5 log10 decline from BL prior to Week 12 but fails to maintain the 0.5 log10 decline from BL with a <1 log10 increase from nadir on any two consecutive scheduled efficacy assessments after Week 12.

Rebound=Patient has a >=0.5 log10 decline from BL by Week 12 that is maintained but viral load remains >=50 copies (not suppressed), followed by >=1 log10 increase from nadir at two consecutive scheduled visits any time after the primary endpoint.

Breakthrough=Patient has suppressed viral load (< 50 copies) at any time after primary endpoint followed by >=200 copies at two consecutive scheduled efficacy assessments.

[4]Suboptimal Response=Patient has a 0.5 log10 decline but does not suppress (<50 copies) at any time after primary endpoint; Virologic Suppression=Patient has a 0.5 log10 decline and does suppress (<50 copies) at any time after primary endpoint

Programming note: See footnotes (values to the left of the =) to indicate what values will be displayed in the listing.

Westat (Created on DDMMMYYYY)
S:\TMB311\DA\SAS\L VLOUTCOMES.SAS

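### SAP 3.3.4 replaces viral loads measured after confirmed virologic failure with the baseline value, so late mean change and mean RNA mix measurements with assigned values

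*SAP*

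**What the plan says.** SAP 3.3.4 (Missing Data Conventions) says the missing-equals-failure (MEF) "imputation technique will be applied to the viral load measures", naming both log10 copies/mL and copies/mL. It then gives two rules. The first: "If a viral load measurement is missing at any scheduled visit, the value will be replaced with the baseline viral load measurement". The second is added to it: "all visits after a confirmed virologic failure will be imputed as failures (replaced with the baseline measurement) for all study visits", with the closing words "for all study visits even if the patient discontinued early".

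Other places describe MEF more narrowly. Protocol 9.2.1.1 says: "Patients with missing effectiveness data at Day 7 will have their effectiveness set to failure for all dichotomous effectiveness variables". SAP 4.4 says MEF applies "with regard to imputing missing viral load results as applicable".

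Protocol 9.2.1.2 provides a supportive mITT analysis of all data with no imputation. SAP 3.2.1 runs an mITT analysis only if some enrolled patient did not receive a complete dose, and does not repeat the no-imputation statement.

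Both documents define virologic failure as two measurements in a row, from Week 24 on, with a decline from Baseline of less than 0.5 log10 (Protocol Summary, Protocol 3.1, SAP 2.1).

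**The concern.** The second rule sits under a missing-data heading but is not limited to missing data. Because the first rule already fills every missing value with baseline, the second changes a result only where a sample was taken and a viral load reported.

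It acts on the continuous values, so it enters the mean change from Baseline (SAP 4.5.2.2), the copies/mL summaries (SAP 4.5.2.1) and the mean plots (SAP 4.5.3). In a study described as primarily descriptive, a mean that combines measured changes with assigned zeros is hard to interpret. It is not reliably conservative either: a patient who responds again is set to no change, and so is a patient whose viral load is above baseline.

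The SAP guarantees no observed-data summary against which a reader could check the effect.

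**Working it through.** The plan states no figure for this rule, so there is nothing to reproduce. The check has four parts.

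**1. Can measured values exist after confirmed failure?** Yes.
- Withdrawal for virologic failure is optional in the Protocol Summary, Protocol 5.3.1 and SAP 2.1, but mandatory in Protocol 3.1.
- Snapshot category 2b in SAP 4.5.2.3 reads "2b=Discontinued efficacy portion of study because of virologic failure (may still continue safety".
- HIV-1 RNA is drawn at Early Withdrawal (Protocol 6.4) and at Week 150 (Tables 3-2, 3-4 and 3-6).

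**2. Which visits are exposed?** Scheduled viral loads from Week 24, taken from those tables:
- Cohort 2: Weeks 24, 28, 36, 48, 60, 72, 84, 96, 108, 120, 132, 144, 150. Failure can be confirmed at Week 28, leaving up to 11 later visits.
- Cohort 1: Weeks 24, 36, 48, 60, 72, 96, 108, 120, 132, 144, 150. Failure can be confirmed at Week 36, leaving up to 9. SAP 4.5.2 extends the secondary endpoints to this cohort.

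These counts use scheduled visits only; Protocol 6.5 also allows an unscheduled confirmatory viral load. In both cohorts the exposed visits include five of the six key visits from Week 24 on: Weeks 48, 72, 96, 120 and 144.

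**3. Effect on mean change.** Let f be the share of patients at a visit with a measured value after confirmed failure, d their mean measured log10 change, and m the mean in everyone else.
- Measured values kept: (1 − f)·m + f·d
- SAP rule: (1 − f)·m + f·0
- Shift = SAP − measured = −f·d. The term in m cancels.

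The documents give neither f nor d, so the ranges below are assumptions. For scale only, m = −1.6, close to the TMB-301 Week 25 result in Protocol 1.2. Example: at f = 20% and d = −2.0, measured = 0.8 × (−1.6) + 0.2 × (−2.0) = −1.68; SAP = 0.8 × (−1.6) = −1.28; shift = +0.40.

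| f | SAP rule | Measured, d = +0.3 | Measured, d = −0.3 | Measured, d = −2.0 |
|---|---|---|---|---|
| 5% | −1.52 | −1.505 | −1.535 | −1.62 |
| 10% | −1.44 | −1.41 | −1.47 | −1.64 |
| 20% | −1.28 | −1.22 | −1.34 | −1.68 |

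Shifts at f = 10% and 20%: −0.03 and −0.06 for d = +0.3; +0.03 and +0.06 for d = −0.3; +0.20 and +0.40 for d = −2.0. For patients still failing with some decline under 0.5 log10, the shift is below 0.5 × f, so under 0.05 at 10% and under 0.10 at 20%.

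**4. Effect on response rates.** If a share r of the failed patients later meet the response criterion, the rate moves by −f·r. At f = 20% that is 0 points for r = 0 and −10 points for r = 50%. This is the difference between two endpoint definitions and not, in itself, an error.

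**The case against.** The strongest reply is that the sentence stands in a missing-data section and SAP 4.4 confines MEF to missing results. It may have been meant only to keep failed patients who left the study in the denominator. That intent is plausible, but the wording does not say so, and the closing clause extends the rule to early leavers without restricting it to them. At the least, 3.3.4 and 4.4 disagree.

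Second, if Protocol 3.1 is followed, few values after failure exist beyond the Early Withdrawal visit. This stands as a limit on size, although Protocol 11.5 has a process for keeping a patient whom the protocol says to discontinue.

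Third, for yes/no endpoints, counting every visit after failure as non-response is a defensible prespecified composite. The snapshot also groups an OBR change with the failure categories. This stands. A reader might infer that the later response rates are simply wrong; they are not, provided the definition is stated.

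A reader might infer two further problems that the documents do not support:
- **That the rule feeds itself**, with two missed samples filled with baseline and then counted as failure. The definition requires two measurements, and a filled-in baseline is not one.
- **That breakthrough triggers it.** The outcome listing does place "Breakthrough=Patient has suppressed viral load (< 50 copies) at any time after primary endpoint" under its virologic failure column, but SAP 4.5.2.3 treats breakthrough as a separate outcome, and a column heading does not override the stated definition.

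Finally, no formal testing is planned (SAP 3.4.2), and measured viral loads may appear in listings. The CD4 listing shows unimputed beside imputed values, and not all listing shells are in the available documents, so it cannot be said that measured viral loads go unreported.

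**Conclusion.** The concern holds for the continuous summaries. As written, SAP 3.3.4 puts baseline in place of measured viral loads after confirmed failure. This goes beyond the protocol's MEF rule and does not match SAP 4.4.

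The direction is not fixed. The rule understates the effect where patients respond again, flatters it where viral load exceeds baseline, and makes little difference where patients continue to fail near baseline. At the larger assumed share, 20%, the range runs from −0.06 to +0.40 log10. These sizes rest on assumed values of f and d. The real f depends on how many patients stay after failure, where the optional and mandatory withdrawal wordings must be reconciled.

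It would be too strong to say that mean change no longer reflects anything observed: measured values up to failure, and those of patients who never fail, are kept. The Day 7 primary endpoint is untouched, because failure cannot be declared before Week 24.

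**What to change.** In the SAP:
1. Use measured values for mean change and for all copies/mL summaries and plots.
2. Limit the post-failure rule to the yes/no endpoints, label it as a composite in which failure is permanent, and stop describing the result as an observed rate in 4.5.2.1.
3. Always present the non-imputed analysis promised in Protocol 9.2.1.2, without the condition in SAP 3.2.1.
4. State that confirmed failure means the protocol definition, judged on measured values before any imputation. This closes off the two readings that the text does not support.
5. Align 3.3.4 with 4.4, whose cross-reference for MEF also points to 3.3.3.

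Separately, reconcile the withdrawal wording in the Protocol Summary, Protocol 5.3.1 and SAP 2.1 with Protocol 3.1.

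The cost is SAP wording and a simpler derivation. Late mean changes may move somewhat in either direction.

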#### 4.5.2.4 CD4+ T-Cell Counts

Summary statistics will be presented for CD4+ T-cell count and change from Baseline in CD4+ T-cell count at the each key visit after Week 12 [Weeks 24, 48, 72, 96, 120, and 144/EOS].

CD4+ T-Cell Counts for all patients at all assessed visits will also be presented in a data listing. The listing will include a column indicating whether or not the patient met the definition of toxicity (2 consecutive laboratory results, at least 14 days apart, with a CD4+ T-cell count below

200 cells/mm^3 that also represents a 50% reduction from the Baseline CD4+ T-cell count).

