## 4.5.3. Graphical Displays

In addition to the tables and listings described above, the following graphical displays of efficacy endpoints will also be included:

- Proportion of patients achieving a ≥ 0.5 log10 decrease from Baseline in viral load at all scheduled visits;
- Proportion of patients achieving  $a \ge 1.0 \log_{10}$  decrease from Baseline in viral load at all scheduled visits;
- Proportion of patients achieving RNA levels < 50 copies/mL at all scheduled visits;
- Proportion of patients achieving RNA levels < 400 copies/mL at each study visit;
- Mean (+/- SE) RNA levels (copies/mL) at all scheduled visits;
- Mean (+/- SE) change from Baseline in RNA levels (copies/mL) at all scheduled visits;
- Mean (+/- SE) CD4+ cell count (cells/mm^3) at all scheduled visits;
- Mean (+/- SE) change from Baseline in CD4+ T-cell count (cells/mm^3) at all scheduled visits.

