#### Listing 16.2.6.2 CD4+ Cell Count (cells/mm^3)

# Unimputed Original Values Imputed with LOCF [5]

Treatment	Patient ID	Visit [1]	Visit Date (Study Day)	CD4+ Cell Count (cells/mm^3) [2]	CD4+ Cell Count Change from Baseline (%)	Toxicity [4]	CD4+ Cell Count (cells/mm^3) [2]	CD4+ Cell Count Change from Baseline (%)
C1:301/800mg	311-XX-XXX	XXXXXXX	DDMONYYYY (XX)	XXX*	XXXX	XXXX	XXX*	XXXX
C2:800mg	311-XX-XXX	XXXXXXX	DDMONYYYY (XX)	XXX	XXXX	XXXX	XXX	XXXX

[1] EOS=End of Study visit conducted at Week 174 (for TMB-301 rollovers)/Week 150 (for all other patients).

[2]\*=below 200 cells/mm^3

[3] Calculated as (visit value - baseline)/baseline\*100%

[4]Toxicity is defined as 2 consecutive laboratory results, at least 14 days apart, with a CD4+ cell count below 200 cells/mm3 that also represents a 50% reduction from the baseline CD4+ cell count.

[5] Missing values are imputed using the Last Observation Carried Forward (LOCF) method.e

Westat (Created on DDMMMYYYY)
S:\TMB311\DA\SAS\L\_CD4.SAS

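### CD4 counts are carried forward with no justification and no stated stopping point, and no observed-data CD4 summary is specified beside them

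*SAP*

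**What the plan says.** SAP 3.3.4 sets a default: "Unless otherwise specified, missing data for subsequent visits will be considered missing at random and will not be imputed". It then gives two variables their own rules. Missing viral load is set back to the baseline value (missing equals failure). For CD4, "If a CD4+ T-Cell Count is missing at any scheduled visit, the value will be replaced with the most recent previous non-missing value". The CD4 rule carries no rationale and names no end point such as last dose, discontinuation or study closure. The viral-load rule in the same section does refer to patients who stop early.

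SAP 4.5.2.4, under secondary efficacy, says "Summary statistics will be presented for CD4+ T-cell count and change from Baseline", at Weeks 24, 48, 72, 96, 120 and 144/EOS. SAP 4.5.3 adds plots of "Mean (+/- SE) CD4+ cell count" and of change from baseline at all scheduled visits. Neither section says whether observed or carried values are used. Listing 16.2.6.2 shows unimputed and LOCF values side by side for each patient. The protocol does not mention LOCF and does not include CD4 in its effectiveness variables (Protocol 3.5 and 9.8).

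**The concern.** LOCF is unbiased for a visit mean only if, on average, CD4 would not have moved after the last value. The SAP does not argue this, and there are reasons to doubt it. Some exits are related to outcome: a confirmed CD4 fall leads to discontinuation (Protocol 7.2.8), and virologic failure is a reason for withdrawal (Protocol 5.3.1). Other exits are administrative. The Protocol Summary lists discontinuation "Upon commercial availability of ibalizumab", which could end follow-up for many patients at about the same time.

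Read literally, the rule keeps patients who have left in the n and standard error at every later visit as though they had been measured. Results are shown for four patient groups plus a total (SAP 3.4.1), so a few leavers could weigh heavily in a small group. The same section says the descriptive statistics will guide judgements of clinical relevance, so a late CD4 mean may be read as evidence of durable benefit.

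**Working it through.** **Plan's own figure.** There is none to reproduce. The documents give no CD4 target, SD, trajectory to Week 144 or expected dropout for TMB-311. Everything below is illustration on stated assumptions.

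**Age of a carried value.** A patient last measured at Week 24 supplies, at Week 144, a value 144 − 24 = 120 weeks old.

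**Share carried forward.** Inputs from Protocol 1.2: TMB-301 had 40 patients and 31 completed Week 25, so 9/40 = 22.5% did not. *Assumption:* that rate continues as a constant hazard. Share at week w = 1 − (31/40)^(w/25). At half the hazard the exponent is halved.

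| Week | Full rate | Half rate |
|---|---|---|
| 48 | 1 − 0.775^1.92 = 38.7% | 1 − 0.775^0.96 = 21.7% |
| 96 | 1 − 0.775^3.84 = 62.4% | 1 − 0.775^1.92 = 38.7% |
| 144 | 1 − 0.775^5.76 = 77.0% | 1 − 0.775^2.88 = 52.0% |

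At the full rate the Week 24 share is 21.7%. So of every 100 values reported at Week 144, about 77 would be carried: 22 from exits by Week 24, 39 (including those 22) from exits by Week 48, and 77.0 − 62.4 = about 15 from exits after Week 96.

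**Shift in a visit mean.** Shift = d × gap, where d is the share carried and gap is the mean carried value minus the mean those patients would have had. With an assumed gap of 30 cells: 0.225 × 30 = 6.8; 0.40 × 30 = 12; 0.77 × 30 = 23.1 cells. The shift is zero if the gap is zero, and it changes sign with the gap. For scale, the mean gain in TMB-301 at Week 25 was 63 cells (Protocol 1.2).

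**Standard error.** With N held fixed by imputation and an equal SD, the ratio of the LOCF to the observed-data standard error is (s/√N) / (s/√(N(1−d))) = √(1−d). This is 0.88 at d = 22.5%, 0.77 at 40% and 0.48 at 77%.

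**Simulation with assumed CD4 paths.** Median baseline is 100 cells. Sixty per cent of patients rise to a mean gain of 110 by Week 144. The rest stay at a gain of 20 or, in row 2, fall by 10 per 24 weeks after Week 24. No exit sample is modelled. The table gives mean change at Week 144; truth is what would have been seen had everyone stayed.

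| Dropout | Carried | Truth | LOCF | Observed cases | Regression under missing at random |
|---|---|---|---|---|---|
| Depends on earlier CD4 | 44% | 74.5 | 60.1 | 94.5 | 75.3 |
| Same, non-responders decline | 48% | 55.9 | 50.0 | 90.4 | 58.2 |
| Unrelated to CD4 | 41% | 74.3 | 67.5 | 74.4 | 74.4 |
| Unrelated, lighter | 23% | 74.5 | 70.8 | 74.3 | 74.3 |

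LOCF is off by 3.7 to 14.4 cells. The regression is within 2.3 cells of the truth throughout. Observed cases alone are worse than LOCF in the first two rows. LOCF errs low here because the assumed overall mean is rising; other paths would give another answer.

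**The case against.** A reader might infer that LOCF contradicts the SAP's own missing-at-random assumption. It does not. The default opens with an exception clause, and the CD4 rule is one of two specified exceptions. A reader might likewise see an inconsistency in resetting viral load to baseline at a visit where CD4 is carried forward. That is a deliberate failure convention for one variable and a different convention for the other, not an error in itself.

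The stronger defence is about size:

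- Carrying forward after a patient has left is the literal reading but is not stated.
- Early Withdrawal procedures include a CD4 count (Protocol 6.4) and are requested whenever possible (Protocol 5.3.2), so the carried value may often date from exit.
- TMB-301 is one 25-week trial of patients starting treatment. Its attrition may not suit Cohort 1 patients already established on the drug.
- No date or number is given for exits on commercial availability.
- Unimputed values are listed per patient, and the toxicity column sits with them.
- Tables report SD, and standard errors appear only on the plots. No formal testing is planned (SAP 3.4.2).
- Some table shells are not in the text available, so an observed-data CD4 table cannot be ruled out.

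All of this stands, and it limits the claim. It does not supply a stopping point, a justification or a described summary on observed data. An exit sample is also still an old value at visits long after exit. In a descriptive study the mean, n and standard error are the result, so the lack of a hypothesis test does not make them unimportant.

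**Conclusion.** The point holds as a weakness of method and specification, of minor to moderate severity. LOCF for CD4 is unjustified and open-ended, and the available text specifies no observed-data summary. Late-visit n would be overstated and the plotted standard errors too small; at equal SD they would be 0.77 times the observed-data value with 40% carried.

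Two stronger readings should be resisted. One is that the late means are known to be biased, or biased in a known direction: the documents give neither the dropout nor the CD4 paths needed, and there is no bias if CD4 has plateaued. The other is that Week 96 to 144 results would mostly restate early values: even at the full assumed rate, about 39 of 100 Week 144 values would date from exits by Week 48. The 39%, 62% and 77% shares rest wholly on the constant-hazard extrapolation from TMB-301; half that hazard gives 22%, 39% and 52%.

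**What to change.** Amend SAP 3.3.4, 4.5.2.4 and 4.5.3 as follows.

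- Make the main CD4 summary a repeated-measures model on observed values, including Early Withdrawal samples, with visit, patient group, baseline CD4 and patient. State that it estimates CD4 as if patients had remained on study; it does not recover CD4 after exit.
- At each visit show n observed, n imputed, the observed mean and a 95% CI. Where a group is too small to model, give observed summaries alone, read with care because observed cases can mislead when dropout depends on CD4.
- Plot observed or model means, labelled as such.
- Keep LOCF as a labelled sensitivity table, and say whether carrying forward stops at discontinuation or administrative closure.

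The cost is SAP wording, one additional standard model and wider intervals at late visits. No data collection changes.
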